### *Analyses & Integration of Mixed Methods Data (Aim 3-Implementation)*

A deductive-inductive rapid qualitative analysis process will be used to facilitate the timely use of qualitative data to refine the implementation strategy, an approach appropriate for the description of implementation processes and environments. Templated summaries of each data collection episode will be created, organizing quotes or observations by pre-established codes (the deductive component) pertaining to RE-AIM domains. Emergent themes in the data (the inductive component) will be captured through use of a grounded theory approach, allowing for discovery of themes not included in a priori codes. Field notes will be written after site visit observations and staff interviews will bolster data not captured in immediate data summaries. An iterative process will occur, in which analysis will begin at the first observation and will inform direction of future data collection. The team will then create a matrix summarizing data by code and collection episode. This will facilitate examination of variation across respondents, identify data gaps, and develop summaries of data mapping onto RE-AIM domains, as well as barriers and facilitators encountered.

## **5.7 Withdrawal of Subjects**

To further ensure the rights of participants and minimize potential risks, participants will be clearly informed that they may withdraw from the study at any time without any repercussions; participants will continue to receive all VA care and rehabilitation services (including supported employment) as usual, regardless of their study status. Withdrawn participants will not be able to continue in audio recorded groups conducted for the purposes of this study nor complete outstanding assessments. If requested upon withdrawal, the participants' data will be removed from the study to the extent possible. If a participant wishes to withdraw, they will be directed to contact the research assistant at their site to provide a reason for withdrawal.

If during the course of the study the participant formally dis-enrolls in supported employment services, their participation in the study will be terminated. We do not anticipate these circumstances occurring often, as they have not occurred in any of our previous studies of CBTw.

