#### *Aim 1 Competitive Work Outcome Measures: Collected Monthly*

The competitive work outcomes are gold standard in VA work studies. In Aim 1, the primary outcome is total weeks worked in competitive jobs. The secondary work outcome is steady competitive work status, defined as working at least 50% of the study period (at least 19.5 weeks out of 38 weeks). Also standard procedure in work studies and used in CBTw pilots, work outcomes will be collected monthly by onsite RAs via Veteran self-report monthly work update form (Appendix 8), and verified with CAPRI/CPRS/JLV SE notes (i.e. SE staff notes will be reviewed for data regarding hours and weeks worked) and directly with SE staff using a data collection form (Appendix 9), as needed. Additional verification layers will be used under any of the following conditions: monthly work update forms are not fully completed; conflicting or unclear information is reported (e.g., Veteran reported only working two days during a month when s/he is employed full time); Veterans report having difficulty recalling their work during the past month. Work outcomes may be collected in person or by phone.

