#### *Aim 2 Health and Recovery Outcomes: Collected at baseline, posttreatment, 6 & 9 months*

Used in the CBTw pilot studies and across the SMI literature, subjective recovery pertinent to work will be measured using the Recovery Assessment Scale (RAS), a 41 item, self-report measure with higher scores indicating stronger recovery attitudes (scored on a 1 to 4 Likert scale); the RAS was developed and validated in people with SMI.

Psychiatric symptoms will be assessed using the adult version DSM-5 Level 1 Cross-Cutting Symptom Measure (CCSM), a 23-item, Likert response (scored on a 0 to 4 scale), self-rated instrument that assesses 13 domains that are important across SMI diagnoses (e.g., depression, anxiety, psychosis, mania, sleep problems, self-harm, substance use, etc.) with higher scores indicating more severe total symptoms. The CCSM has been found to have strong validity and reliability in SMI samples.

Health-related quality of life will be examined using the SF-12 comprised of the Physical Component Summary (PCS) and Mental Component Summary (MCS). The PCS and MCS are standardized with a mean of 50 and a standard deviation of 10, with higher scores indicating better health-related quality of life. The subscales have good reliability and are predictive of health outcomes in Veterans with chronic illness.

Suicidality will be assessed with the 21-item Scale for Suicidal Ideation (SSI), an interviewer rated measure of a continuum of suicidal ideation, including thoughts, attitudes, plans, and behaviors. SSI items are scored on a 0 to 2 Likert scale, with higher scores indicating greater intensity of suicidal ideation. The SSI has strong psychometric properties in outpatients with psychiatric conditions.

Collected from a CAPRI/CPRS/JLV data pull, service utilization data will include days of psychiatric hospitalizations. Lead by [name], this service utilization data will be extracted from the Corporate Data Warehouse.

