Aim 1: Work outcomes. The primary analysis is intention-to-treat and the primary outcome is total weeks worked in competitive jobs with primary endpoints of 6 and 9 months. Power estimate for total weeks worked was calculated using simulated data from a three-level linear regression model to account for the nested structure of the data. Simulation studies are the most flexible method for power analysis which can be tailored to any kinds of analyses. SAS 9.4 was used to generate 1000 datasets from each hypothesized model with plausible effect sizes for parameters of interest based on pilot data. Power estimates are based on the percentage of the datasets (replications) in which the parameters were significant. Based on the open trial pilot data, an ICC of .077 was estimated for the clustering effect of cohort and an ICC of .2 for repeated measures. Our pilot data show that CBTw significantly increased total weeks worked at 6 months ($f^2 = .15$). It is anticipated that there will be a larger increase in total weeks worked over time for the treatment arm. With the target sample size, there will be 97.6% power to detect even a small study arm by time interaction effect ($f^2 = .03$) with type I error set at .05. Further, the outcome distribution is likely to be non-normal. Although power will be attenuated by this non-normality, power to detect the target effects is still expected to be sufficient (>80%). For the binary outcome of achievement of steady competitive work, CBTw pilot data show that 49% of participants who were unemployed at baseline became steady workers at 6 months. In WORKWELL, it is expected that 5-10% more participants will acquire work and become steady workers during by the 9 month follow-up. Thus, power estimates may be conservative. In the control arm, it is anticipated that approximately 34% will become competitively employed and a lesser number will be steady workers by 9 months, based on VHA program evaluation data reporting 1-year SE outcomes. Based on the effect size, simulated data was used from two level logistic regression models, finding that the target sample size will provide > 99% power to detect the treatment effect, accounting for a conservative estimate of 13% attrition. If more participants gain competitive employed in the control arm (~50%), there will be >80% power to detect this effect.

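### Section 5.7 has only all-or-nothing withdrawal, so a Veteran who asks to leave the groups and is processed as withdrawn also loses all later assessments

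*Protocol*

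**What the plan says.** Protocol section 5.7 tells Veterans that "they may withdraw from the study at any time without any repercussions" and gives the consequence in one sentence: "Withdrawn participants will not be able to continue in audio recorded groups conducted for the purposes of this study nor complete outstanding assessments". A Veteran who wants to withdraw is sent to the site research assistant to give a reason. On request, the participant's "data will be removed from the study to the extent possible". Care is unaffected: "participants will continue to receive all VA care and rehabilitation services (including supported employment) as usual, regardless of their study status".

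The SAP, under Sample size and power, states: "The primary analysis is intention-to-treat and the primary outcome is total weeks worked in competitive jobs". Protocol section 5.6 (Study Evaluations) collects weeks worked monthly by self-report. Supported employment (SE) records are used for verification: "SE staff notes will be reviewed for data regarding hours and weeks worked". For psychiatric hospital days, "this service utilization data will be extracted from the Corporate Data Warehouse".

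Section 5.7 also has a second exit, for a Veteran who "formally dis-enrolls in supported employment services, their participation in the study will be terminated". That is a separate matter and is not part of this point.

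**The concern.** An intention-to-treat analysis needs outcomes on everyone randomized, whether or not they took the allocated sessions. A Veteran may want to stop the groups, because they are unhelpful or clash with a new job, and still be willing to fill in a monthly form or take a call. The written procedure gives the research assistant no lesser option to offer and no instruction to ask which part the Veteran wants to stop. Three sites could handle the same request in three ways.

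If the request is recorded as withdrawal, stopping treatment becomes missing primary outcome data. The reasons for leaving may be related to work. Missing-data models then have to cover a period for which the Veteran might have supplied real data.

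**Working it through.** **1. The plan's own power figure.** Inputs from the SAP: N = 276, attrition 13%, f² = .03 for arm by time, type I error .05, ICC .077 for cohort and .2 for repeated measures, stated power 97.6%. From protocol section 5.2.2: up to 8 per cohort.

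- Attrition: 276 × 0.87 = 240.1 and 240/0.87 = 275.9, so N is consistent with losing about 36 Veterans.
- The 97.6% came from a simulation whose time points, variances and handling of attrition are not given, so it cannot be reproduced exactly.
- Approximation: noncentral F with 1 df and λ = f² × n_eff, where n_eff = nT / (D_c × D_r), D_c = 1 + (m − 1) × .077 and D_r = 1 + (T − 1) × .2. Error df are taken as n_eff − 10. T = 3 is an assumption. With 13% loss, m = 8 × 0.87 = 6.96 and D_c = 1.459.

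| n = 240, T = 3 | n_eff | λ | Power |
|---|---|---|---|
| D_r only | 720/1.4 = 514 | 15.4 | 97.5% |
| D_c only | 720/1.459 = 494 | 14.8 | 97.0% |
| Both | 720/(1.459 × 1.4) = 353 | 10.6 | 90.0% |

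Applying either design effect alone comes close to the stated figure. Applying both gives a lower one, and that version is used below.

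**2. Power cost of the loss.** With no attrition, m = 8, D_c = 1.539 and n_eff = 828/(1.539 × 1.4) = 384, so λ = 11.5 and power is 92.3%. At 13% it is 90.0%, at 20% 88.4% and at 30% 85.5%. Between no loss and 13%, power falls from 84.7% to 81.5% with T = 2, and from 95.5% to 93.9% with T = 4. This counts all attrition, with leavers contributing nothing. At the planned 13%, groups-only exits can therefore cost no more than about 2 to 3 points.

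**3. When the data stop.** The groups last 12 weeks, so a groups-only exit normally falls before the 12-week assessment. Taking 6 months as 26 weeks from baseline, an exit after week w leaves 26 − w weeks unobserved:

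- w = 4: 22/26 = 85%
- w = 8: 18/26 = 69%
- w = 12: 14/26 = 54%

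Everyone starts without a competitive job (section 5.5.1), and such a leaver has at most about two monthly forms. The likelihood has little outcome history to work from.

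**4. Why no bias figure is given.** Bias depends on the share of groups-only exits in each arm and on how leavers' later work differs from stayers', given what was observed. The documents give neither. The 13% is total attrition, with no breakdown by cause. The f² of .03 describes an arm-by-time effect, and no SD of weeks worked is stated, so it cannot be turned into a difference in weeks. Even the direction is open: leaving because a job started suggests more work among leavers, while leaving from discouragement suggests less.

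**The case against.** The strongest reply is that section 5.7 governs withdrawal from the study and never equates stopping the groups with withdrawing. Section 5.2.2 allows individual booster sessions after missed CBTw groups. Attendance is tracked and related to outcomes, and the SAP's Reach measures list completion, attendance and attrition separately. This stands. A reader might infer that every Veteran who stops attending is lost, but a non-attender who does not withdraw should still be assessed.

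A reader might also infer that a withdrawn Veteran drops out of the intention-to-treat analysis altogether. That is not supported. Earlier data are kept unless removal is requested. The missing-data sections of both documents plan full information maximum likelihood, pattern-mixture models if missingness is nonignorable, and sensitivity analyses from no work to full employment. What remains is that these methods have little to draw on when the exit comes early.

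Two further inferences go too far. Section 5.7 bars outstanding assessments but is silent on chart or data-warehouse extraction, and the consent pages are not available to check, so a ban on record follow-up cannot be assumed. Nor do SE notes hold the primary outcome in full: they verify self-report, and nothing shows that they are complete without it. Only hospital days come wholly from records.

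Finally, ending contact at a participant's request is a legitimate protection. That supports keeping full withdrawal available. It does not justify making it the only written option.

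**Conclusion.** The point holds in a limited form. The only written voluntary exit ends the groups and the assessments together. When a wish to leave the groups is processed through it, outcome collection stops from that date, with more than half of the 6-month window still to come if the exit falls within the 12 weeks. That is avoidable missing data in an intention-to-treat trial.

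The main issue is possible bias of unknown size and direction. The loss of power is small: 92.3% to 90.0% at 13% attrition, assuming T = 3, cohorts of 8, both design effects and all attrition counted as full loss. It would be tempting to quote a bias in weeks worked from the 13% and the f². The documents do not support such a figure, because the planned analysis is not a completer comparison and the necessary inputs are missing. The change is worth making because it is cheap and uses forms and visits already planned.

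**What to change.** In section 5.7 and the consent script:

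1. State that stopping the groups is not study withdrawal. By default such Veterans continue the monthly work forms and the 12-week, 6-month and 9-month assessments.
2. Limit the bar on outstanding assessments to Veterans who decline further contact.
3. Ask those Veterans whether record extraction may continue, subject to consent: hospital days from the Corporate Data Warehouse, and weeks worked from SE notes as a partial substitute for self-report.
4. Keep full withdrawal, with no further data, available to anyone who wants it.
5. Record the level and date of each exit and report them by arm.

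In the SAP, state that all data collected under items 1 and 3 enter the intention-to-treat analysis.

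The cost is a protocol and consent amendment and a short withdrawal form. No patients or visits are added to the plan. The downside is less detailed work data for Veterans followed through records only.

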### *Standard Care: VHA Supported Employment (SE) Services*

Participants in both study arms will receive standard SE services during the entire study period. SE services are individualized; vocational specialists meet one-on-one with Veterans and provide job assistance tailored to their needs and preferences. SE services are based on the evidence based Individual Placement and Support (IPS) model that includes the following main tenets: a zero exclusion policy, a brief vocational assessment, rapid job search, job development, including dynamic engagement with employers in the community to identify and secure jobs, job carving (i.e. working with employers to create jobs based on veteran needs), integration with mental health services, benefits counseling, and follow-along support after job acquisition. Further, VACO does periodic fidelity assessments to ensure quality at the 3 SE programs (all have good fidelity to IPS model). VISN learning communities supporting IPS implementation are also available.

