To test **Hypothesis 2b**, two-level linear regression models will examine the effects of work on health and recovery outcomes over time, with predictors of competitive weeks worked, time, weeks by time interaction, site membership and potential interaction between site and key predictors, potential covariates (i.e. controlling for baseline levels of health and recovery), as well as random effects to accommodate the potential non-independence due to repeated measures and group cohort effects.

Missing data: Aims 1 & 2

Missing data from Aims 1 and 2 will come in two different forms: missing by attrition and intermittent missing of observation. Using logistic regression, the effects of missing observations due to sample attrition will be examined by investigating the participant characteristics associated with dropout. If results reveal that data are missing completely at random (MCAR) or due to observed factors (MAR), the data will be analyzed using full information maximum likelihood, taking into account potential predictors for missingness. However, if the pattern of missing data is nonignorable, pattern-mixture models that includes variables defined by the participant's pattern of missing data will be used. Sensitivity analyses also will be performed to examine how the result will change based on different assumptions about the missing data, such as the missing work period having no work, the mean amount of work as available data from earlier follow-up periods, or full employment.

Account for Heterogeneity in the Sample

The study is limited to working aged Veterans with SMI who are unemployed at baseline, decreasing the heterogeneity of the sample. In addition, analyses will examine whether treatment effect will change as a function of the site membership and major characteristics of the study participants, such as different types of SMI diagnoses, age, and current substance use (e.g., users vs. non-users).

AIM 3 CBTw IMPLEMENTATION: OVERVIEW

The initial CBTw implementation strategy was informed by implementation science and developed based on our experience in the two CBTw pilots, stakeholder surveys and interviews, and feedback from operational partners. *In order to ensure successful implementation of CBTw during WORKWELL and wide-scale uptake following its completion, an evaluation of this initial implementation strategy and barriers and facilitators of implementation will be conducted, guided by the RE-AIM framework.*

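### Ending study participation when a Veteran leaves supported employment creates avoidable, possibly informative missing outcome data in the intention-to-treat analysis

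*Protocol*

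**What the plan says.** Protocol 5.7 (Withdrawal of Subjects) sets the rule: "If during the course of the study the participant formally dis-enrolls in supported employment services, their participation in the study will be terminated". It adds: "We do not anticipate these circumstances occurring often, as they have not occurred in any of our previous studies of CBTw". Earlier in the section, on voluntary withdrawal, it says: "Withdrawn participants will not be able to continue in audio recorded groups conducted for the purposes of this study nor complete outstanding assessments".

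The SAP (Aim 1: Work outcomes) says: "The primary analysis is intention-to-treat and the primary outcome is total weeks worked in competitive jobs with primary endpoints of 6 and 9 months". The protocol's standard-care section assumes continuous exposure: "Participants in both study arms will receive standard SE services during the entire study period". It lists "follow-along support after job acquisition" among the components of SE.

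Both documents (Missing data: Aims 1 & 2) plan a logistic regression of dropout on participant characteristics. If missingness looks completely random or explained by observed factors, full information maximum likelihood is used. The SAP's alternative reads: "if the pattern of missing data is nonignorable, pattern-mixture models". Three further analyses are planned without any condition. They treat missing work periods as no work, as the mean from earlier periods, or as full employment.

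**The concern.** An intention-to-treat comparison needs outcomes from everyone randomised, whatever services they later use. Here follow-up ends on an event that occurs after randomisation, in the service whose purpose is to produce the primary outcome. Veterans may leave SE because they are settled in work or because they no longer want it. In both cases the unseen weeks would differ from those of Veterans who stay, and the mix of reasons could differ by arm. The estimated difference in weeks worked, and in steady work, could then move either way.

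The loss is avoidable. The primary outcome comes from a monthly self-report form that may be completed by phone, and that does not require SE enrolment.

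**Working it through.** **1. Does the rule stop outcome collection?** The termination sentence does not mention outcome data. The bar on assessments is written for withdrawn participants, who are told that they keep SE. Extending it to those terminated for leaving SE is an inference. It is still the natural reading, since participation is terminated and no section provides for work forms, assessments or record pulls afterwards. Routine verification of work relies on SE notes, with SE staff as needed (Protocol 5.6, Aim 1 measures), so it also weakens after exit.

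**2. Can the missing-data rule recognise the problem?** The distinction between missing at random and nonignorable depends on the unobserved weeks. A regression of dropout on observed characteristics can show which of them predict dropout. It cannot show that missingness is nonignorable, so the step that selects the primary method cannot answer its own question. This applies to all dropout, not only to SE exit.

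**3. What figures do the documents give?** There is no exit rate to reproduce. The nearest figure is attrition of 13%, which leaves 276 × 0.87 = 240 analysable and is not split by reason. Steps 4 and 5 therefore use assumed exit rates.

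**4. Steady work (illustration).** Inputs from the SAP are 49% for CBTw and 34% for control. The 34% is a competitive-employment rate and the SAP expects fewer steady workers, so it is only a stand-in. The true difference is 15.0 points. Assume 10% of the CBTw arm and 5% of control are terminated.
- Leavers all steady workers, scored as no work: (49 − 10) − (34 − 5) = 10.0 points.
- Same leavers, completers only: 39/90 − 29/95 = 43.3% − 30.5% = 12.8 points.
- Leavers all non-workers, completers only: 49/90 − 34/95 = 54.4% − 35.8% = 18.7 points (unrounded).
- Same leavers, scored as full employment: (49 + 10) − (34 + 5) = 20.0 points.

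**5. Weeks worked to week 26 (illustration).** Assume that 49% and 34% get a job, that it starts uniformly between weeks 4 and 20 (mean 12), and that it lasts to week 26. A worker then has 26 − 12 = 14 weeks, and the true difference is (0.49 − 0.34) × 14 = 2.10 weeks.

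If a share q of job-holders leaves SE 4 weeks after starting, each loses 14 − 4 = 10 weeks on average. With p the share who get a job, the arm mean is p(14 − 10q) when missing weeks count as no work, and 14p(1 − q)/(1 − pq) among completers.
- q = 20% in both arms, no work: 0.49 × 12 − 0.34 × 12 = 1.80. Completers: 5.488/0.902 − 3.808/0.932 = 2.00.
- q = 30% CBTw and 10% control, no work: 0.49 × 11 − 0.34 × 13 = 0.97. Completers: 4.802/0.853 − 4.284/0.966 = about 1.2.

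If instead a share g of non-workers leaves, the completer mean is 14p/(1 − (1 − p)g).
- g = 5% CBTw and 20% control: 6.86/0.9745 − 4.76/0.868 = 1.56.
- g = 20% CBTw and 5% control: 6.86/0.898 − 4.76/0.967 = 2.72.

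The direction therefore depends on who leaves and in which arm. With q = g = 0 the difference stays at 2.10.

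**6. What would the planned likelihood analysis do?** The figures in steps 4 and 5 come from simple scoring or exclusion. The planned method retains data up to exit. A simulation assumed 26 weeks, 25% against 40% with any work, SE closing for 30–50% of current job-holders 8 or 13 weeks after job start, large samples, and a multivariate-normal likelihood within arm. With monthly data, true differences of 1.67–1.82 weeks were estimated 0–3% too small. With only two assessment-point totals, the shortfall was 5–23%. A check with a different assumed rate of job loss showed the same pattern. It also showed that exits as early as four weeks after job start leave some shortfall even with monthly data. Exit here depends on observed job history, which favours the likelihood method; exit driven by unseen future work would not be repaired in this way.

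**The case against.** Four points weigh against a larger claim.

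- **Rarity.** The protocol reports no such exits in its earlier CBTw studies. In the open pilot, 49% of those unemployed at baseline became steady workers, so success did not push people out of SE there. Follow-along support also means that getting a job need not end SE. This stands. It is not a guarantee for a three-site trial with work outcomes to 12 months.
- **Intention-to-treat.** A reader might infer that the rule contradicts the intention-to-treat analysis. The documents do not support that. Nobody is removed from the randomised arm, data up to exit stay in the model, and lost follow-up is handled as missing data. The rule weakens the analysis but does not formally contradict it.
- **Size and direction.** A reader might infer a sizeable bias against CBTw. That needs high exit rates among job-holders, which no passage supports, together with no-work scoring or exclusion, which are not the planned primary method. Exits by non-workers can move the result either way.
- **Existing safeguards.** The no-work, earlier-mean and full-employment analyses are already unconditional; only the pattern-mixture step is conditional. None of them names SE exit as a reason for missingness or recovers the lost weeks.

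**Conclusion.** The concern holds in a limited form, as a cheap improvement. Protocol 5.7 most naturally ends outcome collection on a post-randomisation event plausibly related to the primary outcome, and no passage restores it. The size is unknown because no exit rate is documented. It is near zero if exits are as rare as the protocol expects, and the direction is uncertain. The planned likelihood analysis would limit the bias, more so if the monthly work records enter the model than if only assessment-point totals do. The protocol says weeks worked are collected monthly and analysed at the assessment points, so use of the monthly records is not assured.

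Separately, and whatever the number of SE exits, the SAP's choice of primary method rests on a regression that cannot detect nonignorable missingness. No sample-size or power figure changes.

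**What to change.** **Protocol 5.7.** State that SE dis-enrolment is recorded with date and reason. State that outcome follow-up (monthly work form, available record checks and scheduled assessments) continues unless the Veteran withdraws consent. This concerns data collection only; whether such Veterans stay in the study groups is a separate decision for the sponsor. Reconcile the wording with the SAP's intention-to-treat statement.

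**SAP, Missing data.** Make the missing-at-random likelihood analysis primary in every case, using the monthly work data. Keep the logistic regression as a description of dropout. Always run the pattern-mixture analysis as sensitivity, beside the three analyses already planned. Report SE exits by arm, with timing and reason.

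**Cost.** A short amendment with consent wording, and a few extra contacts, which should be very few if exits are rare. Checks against SE notes will be thinner after exit, so self-report carries more weight. The SAP is dated 9/30/2025. If follow-up has largely finished, the SAP change and by-arm reporting remain feasible, although weeks already lost may not be recoverable.
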